- Mild: An event that is easily tolerated by the patient, causing minimal discomfort and not interfering with everyday activities.
- **Moderate**: An event that causes sufficient discomfort and interferes with normal everyday activities.
- Severe: An event that prevents normal everyday activities.

 Note: An AE that is assessed as severe should not be confused with an SAE. Severe is a category utilized for rating the intensity of an event; and both AEs and SAEs can be assessed as severe

An event is defined as 'serious' when it meets at least one of the criteria described in the definition of an SAE, NOT when it is rated as severe.

Assessment of causality

The investigator is obligated to assess the relationship between medical device under investigation, the procedure and each occurrence of each AE/SAE. The investigator will use clinical judgment to determine relationship.

Relationship between an AE/SAE and the medical device under investigation and the procedure should be assessed as:

- Causal: when relationship is beyond any doubt
- Probable: when relationship seems relevant and/or the event cannot be explained by another cause
- Possible: when relationship is weak but cannot be ruled out
- Not related: when relationship can be excluded

Alternative causes, such as underlying disease(s), concomitant therapy, and other risk factors, as well as the temporal relationship of the event to the use of the medical device under investigation, will be considered and investigated.

The investigator will also consult the investigator's brochure in his/her assessment.

For each AE/SAE, the investigator must document in the medical records that he/she has reviewed the AE/SAE and has provided an assessment of causality for AE or SAE.

There may be situations in which an AE/SAE has occurred, and the investigator has minimal information to include in the initial report to Novo Nordisk. However, it is very important that the investigator always makes an assessment of causality for every event before the initial transmission of the SAE data.

The investigator may change his/her opinion of causality in light of follow-up information and send an AE/SAE follow-up report with the updated causality assessment.

124 of 138

The causality assessment is one of the criteria used when determining regulatory reporting requirements.

Final outcome

The investigator will select the most appropriate outcome:

- **Recovered/resolved**: The patient has fully recovered, or by medical or surgical treatment the condition has returned to the level observed when first documented.
- **Recovering/resolving**: The condition is improving, and the patient is expected to recover from the event. This term may be applicable in case of chronic conditions, cancer of AEs ongoing at time of death (where death is due to another AE). Note: for SAEs, this term is only applicable if the patient has completed the follow-up period and is expected to recover.
- **Recovered/resolved with sequelae**: the patient has recovered from the condition but with lasting effect due to disease, injury, treatment or procedure. If a sequela meets an SAE criterion, the AE must be reported as an SAE.
- **Not recovered/not resolved**: the condition of the patient has not improved, and the symptoms are unchanged, or the outcome is no known.

 Note: this term may be applicable in case of chronic conditions, cancer or AEs ongoing at time of death (where death is due to another AE).
- **Fatal**: This term is only applicable if the patient died from a condition related to the reported AE. Outcome of other reported AEs in a patient before he/she died should be assessed as 'recovered/resolved', 'recovering/resolving', 'recovered/resolved with sequelae' or 'not recovered/not resolved'. An AE with a fatal outcome must be reported as an SAE.
- Unknown: This term is only applicable if the patient is lost to follow-up.

Follow-up of AE/SAE/device deficiency

The investigator is obligated to perform or arrange for the conduct of supplemental measurements and/or evaluations as medically indicated or as requested by Novo Nordisk to elucidate the nature and/or causality of the AE/SAE/device deficiency as fully as possible. This may include additional laboratory tests or investigations, histopathological examinations, or consultation with other health care professionals.

New or updated information will be recorded in the originally completed CRF.

The investigator will submit any updated SAE data to Novo Nordisk within 24 hours of receipt of the information.

Reporting of SAEs, Serious Device Deficiencies that could have led to an SAE and serious health threats

Relevant CRFs (AE and safety information forms, device deficiency that could have led to an SAE form) must be forwarded to Novo Nordisk in accordance with Appendix 4 (Data protection).

Initial notification via telephone is acceptable, although it does not replace the need for the investigator to complete the AE, device deficiency that could have led to an SAE and safety information form within the designated reporting time frames:

AE and device deficiency that could have led to an SAE form within 24 hours

Protocol Trial ID: NN7415-4307	CONFIDENTIAL	Date: Version: Status: Page:	25 March 2021 5.0 Final 125 of 138	Novo Nordisk
-----------------------------------	--------------	---------------------------------------	---	--------------

• Safety information form within 5 calendar days

• Both forms must be signed within 7 calendar days after first knowledge by the investigator.

A suspicion of a serious health threat must be indicated in the SAE form or in the device deficiency that could have led to an SAE form.

For device deficiency that could have led to an SAE, a technical complaint form must also be completed, refer to Appendix 7.

Date: Version: Status:

25 March 2021 Novo Nordisk 5.0 Final 126 of 138

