9.3.1 Time period and frequency for collecting AE and SAE information

All AEs will be collected from the first trial-related activity after obtaining informed consent and until end of trial visit, at the time points specified in the flowchart.

All SAEs will be recorded and reported to Novo Nordisk or designee within 24 hours, as indicated in Appendix 5 for the IMP and on demand treatment, and in Appendix 8 for the investigational medical device. The investigator must submit any updated SAE data to Novo Nordisk within 24 hours of it being available.

Investigators are not obligated to actively seek for AE or SAE in former trial patients. However, if the investigator learns of any SAE, including a death, at any time after a patient has been discontinued from/completed the trial, and the investigator considers the event to be possibly/probably related to the investigational trial product or trial participation, the investigator must promptly notify Novo Nordisk.

Status: Page: Final

72 of 138

The method of recording, evaluating and assessing causality of AE and SAE and the procedures for completing and transmitting SAE reports are provided in Appendix 5 for the IMP and on demand treatment, and in Appendix 8 for the investigational medical device.

Timelines for reporting of AEs, including AESIs are listed in Figure 4.

Some AEs require additional data collection via a specific event form. This includes medication errors observed during the trial. The relevant specific events are listed in Table 13 and the reporting timelines in Figure 4.

[figure not shown]

Figure 4 Decision tree for determining the event type and the respective forms to complete with associated timelines

Table 13 AEs requiring additional data collection (via specific event form) and AESIs^a

Event type	AE requiring additional event form	AESI
Thromboembolic events		X
Hypersensitivity reaction	X	
Injection site reaction	X	
Medication error	X	

^aRefer to Section 9.3.6 for reporting details

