9.3.9 Trial stopping rules

If one of the below mentioned criteria is fulfilled, the Novo Nordisk Safety Committee will urgently evaluate all available data and decide on further actions:

- Significant thromboembolic event
- Event of DIC
- Event of TMA
- Death of trial patient which may be related to the trial product

If enrolment is put on temporary hold, relevant data will be submitted to regulatory authorities, according to local regulations, to support restart of enrolment.

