- The following will be provided as paper CRFs to be used when access to the eCRF is revoked or the eCRF is temporarily unavailable:
 - o AE forms
 - o Safety information forms
 - Technical complaint forms (also to be used to report complaints that are not patient related, e.g. discovered at trial site before allocation)
- Corrections to the eCRF data may be made by the investigator or the investigator's delegated staff. An audit trail will be maintained in the eCRF application containing as a minimum: the old and the new data, identification of the person entering the data, date and time of the entry and reason for the correction. If corrections are made by the investigator's delegated staff after the date when the investigator signed the eCRF, the eCRF must be signed and dated again by the investigator.

• The investigator must ensure that data are recorded in the eCRF as soon as possible, preferably within 5 working days after the visit. Once data have been entered, it will be available to Novo Nordisk for data verification and validation purposes.

Monitoring

- The investigator must permit trial-related monitoring, audits, IRB/IEC review, and regulatory agency inspections and provide direct access to source data documents (original documents, data and records). Direct access includes permission to examine, analyse, verify and reproduce any record(s) and report(s) that are important to the evaluation of the trial. If the electronic medical record does not have a visible audit trail, the investigator must provide the monitor with signed and dated printouts. In addition, the relevant trial site staff should be available for discussions at monitoring visits and between monitoring visits (e.g. by telephone).
- Trial monitors will perform ongoing source data verification to confirm that data entered into the eCRF by authorised site personnel are accurate, complete and verifiable from source documents; that the safety and rights of patients are being protected, to monitor drug accountability and collect completed paper CRF pages, if applicable, and that the trial is being conducted in accordance with the currently approved protocol and any other trial agreements, ICH GCP, and all applicable regulatory requirements.
- Monitoring will be conducted using a risk-based approach including risk assessment, monitoring plans, centralised monitoring (remote assessment of data by Novo Nordisk) and visits to trial sites.

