- Not recovered/not resolved: The condition of the patient has not improved, and the symptoms are unchanged or the outcome is not known.
- Fatal: This term is only applicable if the patient died from a condition related to the reported AE. Outcomes of other reported AEs in a patient before he died should be assessed as "recovered/resolved", "recovering/resolving", "recovered/resolved with sequelae" or "not recovered/not resolved". An AE with a fatal outcome must be reported as an SAE.

Protocol Trial ID: NN7415-4307

CONFIDENTIAL

Date: 25 March 2021 Version: 5.0 Status:

Page:

Final 116 of 138 Novo Nordisk

• Unknown: This term is only applicable if the patient is lost to follow-up.

Follow-up of AE and SAE

The investigator is obligated to perform or arrange for the conduct of supplemental measurements and/or evaluations as medically indicated or as requested by Novo Nordisk to elucidate the nature and/or causality of the AE or SAE as fully as possible (e.g. severe hypersensitivity reactions). This may include additional laboratory tests (e.g. skin prick test) or investigations, histopathological examinations, or consultation with other health care professionals. If a patient dies during participation in the trial or during a recognised follow-up period, the investigator should provide Novo Nordisk with a copy of autopsy report including histopathology.

New or updated information will be recorded in the eCRF.

SAE reporting via eCRF

- Relevant forms (AE and safety information form) must be completed in the eCRF.
- For reporting and sign-off timelines, see box below.
- If the eCRF is unavailable for more than 24 hours, then the site will use the paper AE form and if the eCRF is unavailable for more than 5 calendar days then the site will use the safety information form (see box below).
- The site will enter the SAE data into the eCRF as soon as it becomes available, see 9.3.1.
- After the trial is completed at a given site, the eCRF will be decommissioned to prevent the entry of new data or changes to existing data. If a site receives a report of a new SAE from a patient or receives updated data on a previously reported SAE after eCRF decommission, then the site can report this information on a paper AE and safety information form (see box below) or to Novo Nordisk by telephone.

SAE reporting via paper CRF

- Relevant CRF forms (AE and safety information form) must be forwarded to Novo Nordisk either by fax, e-mail

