- Initial notification via telephone is acceptable, although it does not replace the need for the investigator to complete the AE and safety information form within the designated reporting time frames (as illustrated in Figure 4 in Section 9.3):
 - AE form within 24 hours.
 - Safety information form within 5 calendar days.
 - Both forms must be signed within 7 calendar days.

Contact details for SAE reporting can be found in the investigator trial master file.

Novo Nordisk

[figure not shown]
Date: Version: Status: Page:

25 March 2021 Final 117 of 138

Sports ratings by activity Appendix 6

As per US National Hemophilia Foundation brochure for haemophilia patients, PlayingItSafe.

Table of Activity Ratings

Protocol Trial ID: NN7415-4307

CONFIDENTIAL

Date: Version: Status: Page:

25 March 2021 | Novo Nordisk 5.0 Final 118 of 138

Activity	Ca	tegory			Page
Mountain Bilding			2.5		42
Pilates	1.	5–2			44
Power Lifting				3	44
Racquetball			2.5		44
River Rafting		2			43
Rock Climbing, Indoor or Challenge/Ropes Course	1.	5–2			45
Rock Gimbing, Outdoor			2-3		45
Rodeo				3	46
Rowing	1.5				43
Rowing Machine (Training Equipment)	1.5				27
Rugby				3	46
Running/Jogging		2			47
Scooters, Motorized		2-	-2.5		48
Scooters, Nonmotorized		1.5-2.5			48
Scuba Diving		2-	-2.5		49
Skateboarding		1.5-2.5			50
Skating, ke		1.5-2.5			49
Skating, Inline and Roller		1.5-2.5			50
Skiing, Cross-Country		2			50
Skiing, Downhill			2.5		51
Sking, Water		2-	-2.5		51
Ski Machine (Training Equipment)	1.5				27
Snorkeling 1					ΣQ
Snowboarding			2.5		52
Snowmobiling				3	53
Soccer			2-3		53
Softball		15-2.5			22
Stationary Bike (Training Equipment)					27
	1-15				28
Strength Training/ Resistance Training/ Weight Lifting	1.5				54
Surfing		2-	-2.5		54
Swimming 1					55
Tee-Ball	1.5				22
Tennis		2			55
Track and Field			-2.5		56
Trampoline				5-3	56
Treadmill (Training Equipment)	1.5				28
Volleyball		2-	-2.5		57
Walking 1					58
Water Polo			2.5		58
Wrestling				3	59
Yoga	11	5-2			59
ioya	E 100	/-A			

Date: 25 March 2021 Novo Nordisk
Version: 5.0
Status: Final

Page:

Final 119 of 138

Appendix 7 Technical complaints: Definition and procedures for recording, evaluation, follow-up and reporting

Technical complaint definition

- A technical complaint is any written, electronic or oral communication that alleges product (medicine or device) defects. The technical complaint may be associated with an AE but does not concern the AE itself.

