- Technical complaints include the definition of device deficiency, please refer to Appendix 8

Examples of technical complaints:

- Problems with the physical or chemical appearance of trial products (e.g. discoloration, particles or contamination).
- Problems with packaging material including labelling.
- Problems related to medical devices (e.g. to the injection mechanism, dose setting mechanism, push button or interface between the pen-injector and the needle).
- Problems related to concizumab-ELISA (e.g. uncertain results).

Time period for detecting technical complaints

All technical complaints, which occur from the time of receipt of the product at trial site until the time of the last usage of the product, must be collected for products predefined on the technical complaint form.

Reporting of technical complaints to Novo Nordisk

Contact details (fax, e-mail and address) for Customer Complaint Center – refer to Attachment I Technical complaints must be reported on a separate technical complaint form:

- For concizumab pen-injector: One technical complaint form must be completed for each affected DUN
- For concizumab-ELISA: One technical complaint form must be completed for each onset

For medical device under investigation (concizumab-ELISA), evaluate on the technical complaint form if the technical complaint could have led to an SAE. If the technical complaint on a medical device under investigation could have led to an SAE, a device deficiency that could have led to an SAE form must be completed as described in Appendix 8.

Timelines for reporting of technical complaints to Novo Nordisk

The investigator must complete the technical complaint form in the eCRF within:

- 24 hours if could have led to an SAE (for concizumab-ELISA)
- 24 hours if related to an SAE
- 5 calendar days for all other technical complaints

If the eCRF is unavailable or when reporting a technical complaint that is not patient related, the information must be provided on a paper form by fax, e-mail or courier to Customer Complaint Center, Novo Nordisk, within the same timelines as stated above. When the eCRF becomes available again, the investigator must enter the information on the technical complaint form in the eCRF.

Follow-up of technical complaints

The investigator is responsible for ensuring that new or updated information will be recorded on the originally completed form

Protocol Trial ID: NN7415-4307

CONFIDENTIAL

 Date:
 25 March 2021

 Version:
 5.0

 Status:

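### Appendix 5 sends sites to paper SAE forms only once an eCRF outage has lasted as long as the reporting limits themselves, which conflicts with those limits and with Appendix 4

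*Protocol*

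**What the plan says.** **Fallback rule.** Protocol Appendix 5, under SAE reporting via eCRF, ties the move to paper to the length of the outage. For the AE form: "If the eCRF is unavailable for more than 24 hours, then the site will use the paper AE form". For the second form: "if the eCRF is unavailable for more than 5 calendar days then the site will use the safety information form".

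**Limits.** Section 9.3.1 requires: "All SAEs will be recorded and reported to Novo Nordisk or designee within 24 hours". Appendix 5, under SAE reporting via paper CRF, repeats the AE form limit ("AE form within 24 hours") and allows 5 calendar days for the safety information form. It also covers the telephone: "Initial notification via telephone is acceptable, although it does not replace the need for the investigator to complete the AE and safety information form" within those time frames.

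**Two other rules for the same situation.** Appendix 4, item 9 (Data quality assurance, Case Report Forms), introduces a list that includes the AE form and the safety information form: "The following will be provided as paper CRFs to be used when access to the eCRF is revoked or the eCRF is temporarily unavailable". It sets no minimum outage. Appendix 7 handles technical complaints during an outage by moving them to paper "within the same timelines as stated above", with entry in the eCRF once it is back.

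**The concern.** A fallback exists so that a deadline can be met when the usual route fails. In Appendix 5 the fallback starts only after the system has been down for longer than the whole deadline, for both forms. Appendix 5 is the SAE-specific instruction, so it is the text a site is likely to consult during an outage. Appendix 4 gives it a different answer.

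What is at stake is the timeliness of the completed forms for the events the restarted trial most needs to see. Section 9.3.1.1 requires thromboembolic events to be reported on exactly these two forms. Under section 9.3.9, a single significant thromboembolic event, DIC or TMA means that "the Novo Nordisk Safety Committee will urgently evaluate all available data and decide on further actions". The plan should not contain an instruction that, followed to the letter, can carry a site past its own limit.

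**Working it through.** No sample size, power or type I error figure is involved. The check is a comparison of clocks.

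**Inputs**

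- AE form limit: 24 hours (section 9.3.1; Appendix 5).
- Paper AE form trigger: outage longer than 24 hours (Appendix 5).
- Safety information form limit: 5 calendar days (Appendix 5).
- Paper safety information form trigger: outage longer than 5 calendar days (Appendix 5).
- Start of the clock: taken as awareness of the event. This is an assumption. Section 9.3.1 and Appendix 5 give the durations and point to Figure 4, which is not shown in the text available. Appendix 8 counts the signing of device-event forms from the investigator's first knowledge, which makes the assumption plausible.

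**Formula, AE form.** Put awareness at hour 0 and the limit at hour 24. Let the outage start at hour s, negative if it began before awareness. The Appendix 5 trigger is met just after hour s + 24. The time left for paper is 24 − (s + 24) = −s hours.

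| Outage starts (h from awareness) | Paper trigger met just after hour | Time left to the 24 h limit |
|---|---|---|
| −12 | 12 | 12 h |
| −6 | 18 | 6 h |
| 0 | 24 | 0 h |
| 6 | 30 | −6 h |
| 12 | 36 | −12 h |
| 23 | 47 | −23 h |

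So if the outage began before awareness, some time remains. If it begins at or after awareness (0 ≤ s < 24) and runs past hour 24, the Appendix 5 paper route does not open in time.

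**Shorter outages.** An outage can pass the limit without ever exceeding 24 hours. If it ends at hour e > 24 with e − s ≤ 24, the paper trigger is never met and the form waits for the eCRF. The lateness is then e − 24. Example: s = 6 and e = 28 is a 22-hour outage, and the form is at least 28 − 24 = 4 hours late. In general the lateness is about the smaller of s and e − 24.

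**Safety information form.** The pattern is the same in days: 5 − (s + 5) = −s. An outage starting on day 1 meets the trigger after day 6, 1 day late. One starting on day 3 meets it after day 8, 3 days late. The upper end is just under day 10, almost 5 days late.

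**Condition on all of this.** The form must not have been entered before the outage. When s > 0 the site had s hours (or days) of working eCRF in which to enter it.

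**The provisions side by side**

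| Place | Applies to | When paper is used |
|---|---|---|
| Appendix 4, item 9 | AE and safety information forms | any temporary unavailability |
| Appendix 5 | AE form for SAEs | outage longer than 24 hours |
| Appendix 5 | safety information form | outage longer than 5 calendar days |
| Appendix 7 | technical complaints | on unavailability, limits unchanged |

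Of these, only Appendix 5 adds a wait.

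**The case against.** The strongest reply is that the protocol, read as a whole, already lets a site report on time. Appendix 5 says when paper will be used. It does not say that paper may be used only then, and Appendix 4 supplies both forms for any temporary outage. A reader might infer that sites are barred from paper during the first 24 hours; the documents do not support that. What remains is that two instructions cover the same situation and lead to different actions, and the one specific to SAEs is the slower.

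The second reply concerns consequences. A reader might infer that the urgent evaluation in section 9.3.9 would be delayed. That is not established. The section refers to all available data and does not make a completed form the trigger, and a telephone call can reach the sponsor within 24 hours. This stands: the form may be late, but the notification need not be.

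The third reply concerns size. Lateness of almost 24 hours requires that the site had a working eCRF for almost 24 hours after awareness and did not use it; at s = 0 the lateness is about zero. This also stands, so the upper end is a worst case and not a typical delay.

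Finally, a reader might infer from Appendix 7 that less urgent reports have the quicker fallback. That fits only the complaints with a 5-calendar-day limit. Complaints related to an SAE, and those on the concizumab ELISA that could have led to one, also carry a 24-hour limit.

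**Conclusion.** The point holds as an internal conflict. The waits in Appendix 5 equal the full form limits of 24 hours and 5 calendar days, and they disagree with Appendix 4. A site that follows Appendix 5 literally can submit the AE form up to almost 24 hours late, and the safety information form up to almost 5 days late. This happens when the outage starts at or after awareness, runs past the limit, and the form was not already entered.

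The stronger statement, that an outage makes the SAE report late, does not follow. A site using Appendix 4 can be on time, and telephone notice remains open, although it does not replace the form.

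The timing rests on the clock starting at awareness. The documents do not give outage frequency, so no expected number of late forms can be stated. No estimate, test or error rate in the trial is affected. This is a minor point that is worth correcting because the correction is simple.

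**What to change.** Reconcile Appendix 4 (item 9) with the two SAE reporting parts of Appendix 5 by deleting the outage-length triggers and using the Appendix 7 approach. For example: if the eCRF is unavailable, the site sends the paper AE form within 24 hours and the paper safety information form within 5 calendar days, and enters the data in the eCRF once it is available again. Check at the same time that Figure 4 states when the clock starts.

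The cost is one sentence in Appendix 5. The paper forms are already provided under Appendix 4, and Appendix 5 already expects SAE data to be entered in the eCRF later. The downside is occasional double entry after short outages.
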